Estimation of Event Rates. The table below displays the 90% exact binomial confidence intervals based on 12 patients treated.

No. of Events	%	90% exact CI	No. of Events	%	90% exact CI
0	0.0	17.5*	7	58.3	31.5 , 81.9
1	8.3	.43 , 33.9	8	66.7	39.1 , 87.7
2	16.7	3.0 , 43.8	9	75.0	47.2 , 92.8
3	25.0	7.2 , 52.7	10	83.3	56.1 , 97.0
4	33.3	12.3 , 60.9	11	91.7	66.1 , 99.6
5	41.7	18.1 , 68.5	12	100.0	82.5*

CONFIDENTIAL

6	50.0	24.5 , 75.5	* 90% 1-sided CI
---	------	-------------	------------------

6.2 PHASE II STUDY

Design and Objectives:

This stratified phase II trial is designed to evaluate early complications (e.g., wound complication in pre-operative patients) and late complications (e.g., fibrosis, joint stiffness and edema in post-operative patients). Patients with STS of the lower extremity only will be treated in the phase II study. Justification for enrolling lower extremity STS in phase II is that 80% of STS patients treated in the Department of Radiation Oncology have lower extremity STS and they are the subgroup who may benefit most from protons. For example in the study by O’Sullivan et al (Lancet 359, 2002), in pre-operative patients, the wound complication rate from photon radiotherapy in patients with lower extremity STS was 43% (30 events in 70 patients) compared to 5.5% (1 event in 18 patients) in upper extremity STS. 40 evaluable patients (including evaluable patients from the feasibility stage) will be enrolled in each stratum.

Endpoints:

Same endpoints as in Section 6.1: Wound complication, Fibrosis and joint stiffness, Edema, Acute toxicity, Late toxicity and Clinical Efficacy.

Evaluable for analysis:

For pre-operative patients, patients must have a minimum of 4 months of follow-up post-surgery to be evaluable and included in the phase II analysis. For post-operative patients, patients must have a minimum of 2 years of follow-up from the end of radiotherapy to be evaluable and included in the phase II analysis.

Rules for Early Termination for Wound Complications:

We will assume a beta (2,4) prior, which is information equivalent to wound complication in 2 of 6 treated patients. A wound complication rate >40% is considered unacceptable. If the number of patients with wound complications is greater than or equal to the number in the table below then termination will be considered as it is likely that the wound complication rate is >40%, as noted by the Bayesian posterior probabilities.

Bayesian Rule for Wound complication						
Patients treated & followed 4 months	1	2	2	3	3	4
Patients who experience wound complication	5	0	5	0	5	0
Posterior Prob[wound complication toxicity rate >40%]	8	1	1	1	1	1
		1	3	5	7	9
	0	0	0	0.	0.	0.
	.	.	.	8	7	7
	7	8	8	1	9	8
	6	5	2			
Action	Terminate enrollment					

6.3 STATISTICAL ANALYSES

Pre-operative patients: Toxicity data will be graded and tabulated. A one-sample one-sided chi-square test will be performed to test the null hypothesis that the wound complication rate is 45% (same as photon). Patients must have a minimum of 4 months of follow-up after surgery to be evaluable for this analysis.

CONFIDENTIAL

This material is the property of the University of Pennsylvania. Do not disclose or use except as authorized in writing by the study sponsor

Post-operative patients: Toxicity data will be graded and tabulated. In the study by Davis et al (Radiother and Oncol 75, 2005), the grade 2+ fibrosis rate was 48%, joint stiffness 23% and edema 23%. Since fibrosis is the most common post-operative toxicity, it is considered the primary endpoint and a one-sample one-sided chi-square test will be performed at the 5% significance level to test the null hypothesis of 50% (same as photon). Joint stiffness and edema are less frequent toxicities and will be treated as secondary endpoints. The null hypothesis is that the grade 2 or higher rate is 25% (same as photon) for these endpoints. Patients must have a minimum of 2 years of follow-up after surgery to be evaluable for this analysis.

Acute toxicity (Late toxicity): Toxicities will graded and tabulated by stratum.

Clinical Efficacy: For pre-operative patients, the RECIST response rate (CR + PR based on RECIST) and 90% exact CI will be computed. For each stratum, time to local recurrence, time to distant recurrence, PFS and OS will be estimated by Kaplan-Meier analysis.

Exploratory Analyses of [¹⁸F]-EF5:

The relationship between pre-treatment hypoxia as determined by F18-EF5 scanning and treatment outcome will be examined, stratified by pre- and post-operative cohorts. The clinical outcomes are: RECIST response rate (pre-operative patients only), time to local recurrence, time to distant recurrence, PFS and OS. We hypothesize that high ¹⁸F-EF5 signal of the primary tumor (e.g. high levels of hypoxia) will relate to poorer clinical outcome (lower response rate, shorter time to local recurrence, shorter time to distant recurrence, shorter PFS, and shorter OS) in this group of patients. We will examine the prognostic values of hypoxia, as measured by ¹⁸F-EF5, summarized from regions of the primary tumors. These analyses will be stratified by pre- or post-operative cohorts. Each subject will have summary statistics for hypoxia using ¹⁸F-EF5 PET available from the primary tumor for this analysis. The Kaplan-Meier method will be applied to estimate the distribution of time-to-event outcome variables for patients with ¹⁸F-EF signal above or below median of the summarized values. The association between RECIST response and hypoxia (binary coding) will be assessed by chi-square test. The association between time-to-event outcomes and hypoxia will be established by the Cox proportional hazards models. Both binary and continuous summary measures of ¹⁸F-EF5 signal will be evaluated. A binary indicator for a hypoxic tumor can be defined as ¹⁸F-EF5 signal above versus below median signal or based on other previously defined cut points. The direction and magnitude of the association will be assessed by hazard ratio and its 95% confidence interval.

6.4 SAMPLE SIZE/POWER AND TRIAL DURATION.

With 12 patients per year enrolled to each stratum and accounting for required follow-up time for feasibility and toxicities, this study should be active for 7 years. Twelve pre-operative and 12 post-operative patients will be enrolled on the feasibility portion of the trial. If feasibility and safety are acceptable then 40 evaluable pre-operative patients and 40 evaluable post-operative patients with STS of the lower extremity (each group includes evaluable patients from the feasibility stage) will be enrolled in the phase II portion of the trial. Up to 50 pre-operative patients may need to be enrolled to yield 40 evaluable patients with lower extremity STS who undergo surgery and have 4 months of follow-up post-surgery. With 40 evaluable patients, there will be 84% power for a chi-square test at one-sided 5% type I error to test a grade 2 or higher wound complication rate of 45% versus an alternative rate of 25%.

Similarly, up to 50 post-operative patients may need to be enrolled to yield 40 evaluable patients with lower extremity STS who receive post-operative radiotherapy and remain on-study for 2 years from the end of radiotherapy. With 40 evaluable patients, there will be 83% power for a chi-square test at one-sided 5% type I error to test a grade 2 or higher fibrosis rate of 50% versus an alternative rate of 30%. In addition, there will be 80% power for chi-square tests at one-sided 2.5% type I error to test grade 2 or higher joint stiffness and

CONFIDENTIAL

edema, each with rates of 25% versus alternative rates of 9%. These secondary analyses will be tested at a 2.5% significance level, to control the overall type I error.

All correlative analyses of hypoxia and clinical outcome are exploratory. Results from this unique study will be used to estimate the magnitude of the associations for both RECIST response and time-to-event outcomes and will provide important guidance for future studies of the prognostic importance of hypoxia in STS patients.

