2 SUBJECT SELECTION AND WITHDRAWAL

This study plans to enroll 80 evaluable subjects (40 evaluable patients in each cohort) over 7 years. For pre-operative patients, evaluability requires a minimum of 4 months of follow-up after surgery. For post-operative patients, evaluability requires a minimum of 2 years of follow-up from the end of radiotherapy.

Inclusion Criteria

- Patients with a histologic diagnosis of soft tissue sarcoma of the extremities are eligible for this study.
- Patient must be ≥ 18 years of age.
- Patients must have evidence of disease limited to the extremities.
- For the pre-operative group, patients must be considered operable/resectable and a candidate for pre-operative radiotherapy as judged by the attending surgeon and radiation oncologist. The clinical evaluation of patients will include a work up as per the standard of care. All patients in the pre-operative group will be evaluated for this protocol PRIOR to the initiation of therapy.
- For the post-operative group, patients must be considered operable/resectable (if evaluated prior to resection) and a candidate for post-operative radiotherapy by the attending surgeon and radiation oncologist. The clinical evaluation of patients will include a work up as per the standard of care. Patients in the post-operative group may be evaluated PRIOR to the initiation of any therapy or may be referred for evaluation after surgical resection.
- ECOG status of 0-2.
- Patients must sign a document that indicates that they are aware of the investigative nature of the treatment of this protocol, and the potential benefits and risks. Patients unwilling or unable to sign informed consent are excluded from the study.
- Women of child-bearing potential as long as she agrees to use a recognized method of birth control (e.g. oral contraceptive, IUD, condoms or other barrier methods etc.). Hysterectomy or menopause must be clinically documented.
- Negative urine pregnancy test for females of childbearing potential on the day of the F18-EF5 PET scan prior to F18-EF5 injection

Exclusion Criteria

- Pregnant women, women planning to become pregnant and women that are nursing.
- Patients who experience surgical complications that prevent radiation from starting for 5 months or more, unless there is evidence of gross residual disease.

Subject Recruitment and Screening

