At the University of Pennsylvania, we see approximately 20 cases of extremity STS per year. We anticipate that with the availability of proton radiotherapy, these numbers may increase. We estimate an annual accrual of 12 subjects per year for each cohort. We will also treat patients either preoperatively or postoperatively from Walter Reed Army Medical Center. In addition, this protocol will be listed on our web site as a formal protocol and information of its availability will be made known to treating professionals throughout our satellites as well as other referring physicians. These patients, if treated preoperatively with radiation therapy, will be required to have their surgery at the Hospital of the University of Pennsylvania.

Early Withdrawal of Subjects

When and How to Withdraw Subjects?

Recurrent or Progressive Disease: Subjects who have clinical or radiologic evidence of recurrent disease will undergo an evaluation to document the nature of the abnormality. If recurrent or progressive cancer is diagnosed, the subject will be considered off study at that time.

Subject Participation: Subjects may be withdrawn if the subject decides to refuse continuation of treatment or follow-up. Subjects may also be withdrawn for non-compliance with the protocol or withdrawal of consent. The reasons for withdrawal will be documented.

PI Decision: Subjects may be withdrawn at any time during the study if the PI believes it is in the subject's best interest. In this event, the reasons for withdrawal will be documented.

Once the subject has discontinued treatment, the primary reason for discontinuing treatment must be clearly documented in the subject's records and on the CRF. The investigator will assess each subject for response at the time of withdrawal.

Every effort will be made to follow subjects off study for toxicity and survival. Survival will be followed for a minimum of 5 years by means of scheduled appointments and available medical records. Every effort will be made to follow for overall survival.

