5 STUDY PROCEDURES

	Pre-treat	Day of F18-EF5 PET/CT Prior to injection	Weekly during RT	Visit prior to surgery	30 days post surg/RT ^{1*}	Q3 months for 2 years, then q6 months for years 3 - 5 after surgery/RT	Yearly (as long as the patient wishes to be followed)
Tests and Observations							
History and PE	X		X	X	X	X	X
ECOG PS	X						
Biopsy	X						
Urine Pregnancy Test		X ²					
Toxicity Assessment	X		X			X	
Tumor Measurement	X ¹			X		X	
18F-EF5 PET Scan (optional)	X ³						

1- *Post radiation/surgery follow-up schedule defined for each cohort in Section 6.

2- Urine pregnancy test is routinely performed prior to PET/CT scanning as departmental standard.

3 – Subjects may participate in study with or without performing 18F EF5 PET scan. This is a subject option.

Post-treatment Evaluation and follow-up

All subjects will be evaluated prior to initiation of treatment and weekly during the course of radiotherapy. For patients receiving pre-operative radiation, a visit will occur prior to surgery. This visit will involve an interval history and physical. All patients will be seen for a first post-operative/post-radiation office visit with either the attending radiation oncologist or surgeon no more than 30 days following surgery/radiotherapy or discharge from the hospital, whichever comes later. Pre-operative patients will be seen after surgery, weekly x 1 month, then every 2nd week x 1 month, then monthly for 3 months. Post-operative patients will be seen one month after surgery and then in 3 months. Follow up visits for pre-operative and post-operative patients will be with either the attending surgeon or radiation oncologist every 3 months for two years, and every 6 months thereafter for 3 years. These office follow-up visits will consist of an interval history and physical and imaging studies as clinically indicated. The wound complication endpoint will be scored at 4 months after surgery in the pre-operative group. Post-operative patients will be scored for fibrosis, edema and joint stiffness within 2 years after after radiation.

Assessment of Tumor Response

Tumor Response (RECIST criteria): RECIST criteria will only be evaluated after radiation just prior to surgery in the pre-operative patients. Post-operative patients will not be evaluated since they undergo complete resection of STS.

Target Lesions:

- **Complete Response (CR):** Disappearance of all target lesions.

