Patient cannot be given treatment because anatomy is such that a dosimetrically satisfactory treatment plan cannot be devised. For example, the dosimetry is unsatisfactory if <95% of target volume is covered by 95% of the dose.

Patient is unable to tolerate 25% of treatments using proton radiotherapy, that is, up to 25% of treatments could be delivered using photons. Reasons for missed treatments may include: unable to set patient up within acceptable limits of tolerance, patient unable to tolerate treatment position or immobilization for duration of treatment).

Patient is unable to complete all of his/her treatments within 10 days of estimated date of treatment completion or requires a treatment break greater than 5 days.

(ii) **Acute toxicity** is defined as any grade 3 or higher hematologic or non-hematologic toxicity that is probably or definitely related to radiotherapy (not surgery). All toxicities observed within 90 days from start of radiotherapy, will be graded by NCI CTC Version 4.0. For pre-operative patients all toxicities observed within 90 days after start of radiation treatment or 30 days after surgery, whichever comes later, will be graded.

Secondary Endpoints:

(i) **Late toxicity** is defined as any grade 3 or higher hematologic or non-hematologic toxicity which occurs after 90 days from start of therapy. Late toxicities will be graded according to the RTOG/EORTC late toxicity criteria. The time frame for late toxicity is open-ended and late toxicities have been known to occur a year or more after therapy. Follow-up for late toxicity will cease when a patient experiences disease progression, since 2nd line therapies may then be initiated.

(ii) **Wound complication** is defined as a secondary operation under general or regional anesthesia for wound repair or wound management without second operation. Wound management includes an invasive procedure without general or regional anesthesia, readmission for wound care such as iv antibiotics, or persistent deep packing for 120 days or longer. Patients will be assessed for wound complications which develop within 4 months after surgery.

(iii) **Fibrosis and joint stiffness** will be graded according to EORTC/RTOG late radiation toxicity criteria. **Edema** will be graded as 0= none, 1= mild, 2= moderate, 3= severe, 4= very severe, according to the criteria of Stern (Stern TN. Clinical examination: a textbook. Year Book Medical

CONFIDENTIAL

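### The pre-operative Phase II primary test drops operated patients with under 4 months of follow-up even when a wound complication is already recorded, which can bias the rate in either direction

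*Combined protocol and SAP*

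**What the plan says.** The pre-operative endpoint, defined under Endpoints in section 6.1 and carried into Phase II by section 6.2, covers a second operation for wound repair, an invasive wound procedure, readmission for wound care, and deep packing that lasts at least 120 days. On timing: "Patients will be assessed for wound complications which develop within 4 months after surgery". Section 5 adds: "The wound complication endpoint will be scored at 4 months after surgery in the pre-operative group".

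Entry to the analysis depends on completed follow-up, and three places agree:
- Section 2: "For pre-operative patients, evaluability requires a minimum of 4 months of follow-up after surgery".
- Section 6.2: "patients must have a minimum of 4 months of follow-up post-surgery to be evaluable and included in the phase II analysis".
- Section 6.3, for the primary test itself: "Patients must have a minimum of 4 months of follow-up after surgery to be evaluable for this analysis".

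None of these keeps a patient whose complication is recorded before month 4. None says what happens to a patient who dies, withdraws or is lost in that window. Section 6.3 tests a null rate of 45% with a one-sided one-sample chi-square test. Section 6.4 sets the level at 5%, the alternative at 25%, the size at 40 evaluable patients and the power at 84%, and allows up to 50 enrolled to reach 40.

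**The concern.** The Phase II objective in section 1 is the wound complication rate after pre-operative proton radiotherapy. Most components of the endpoint can be established weeks before month 4. The analysis set is nevertheless fixed by something that happens after surgery, namely staying in follow-up. Suppose a patient is reoperated on at week 5 and leaves at week 12. The patient has had the event, yet read literally is not evaluable. The test then describes patients retained for 4 months, not patients operated on.

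What is at stake is the primary conclusion. With 40 patients, the result can turn on one or two people. If complicated patients are lost more often than others, the test rejects 45% too readily. If they are lost less often, it loses power. A rule that discards observed outcomes also invites a decision on such patients after the results are known.

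**Working it through.** **Inputs.** From sections 6.3 and 6.4: n = 40, null p0 = 0.45, alternative p1 = 0.25, one-sided 5%. The shares of patients lost early are assumptions, because the documents give none.

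**1. The plan's own figure.** Power = Φ[(0.20·√40 − 1.645·√(0.45·0.55)) / √(0.25·0.75)] = Φ[(1.265 − 0.818)/0.433] = 84.9%, against the stated 84%. The figure reproduces.

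**2. Rejection threshold.** z = (0.45 − x/n)/√(0.45·0.55/n). At 12/40, z = 1.91 (p = 0.028); at 13/40, z = 1.59 (p = 0.056). The test rejects at 12 or fewer. Exact size is P[Bin(40, 0.45) ≤ 12] = 3.9%; exact power is P[Bin(40, 0.25) ≤ 12] = 82.1%.

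**3. Restoring recorded complications, planned chi-square test.** Add k patients to both numerator and denominator.
- From 12/40: 13/41 gives z = 1.71 (p = 0.044, still rejects); 14/42 = 33.3% gives z = 1.52 (p = 0.064, no longer rejects).
- From 10/40, the result expected under the alternative: 12/42, 13/43 and 14/44 give z = 2.14, 1.95 and 1.76, all still rejecting; 15/45 gives z = 1.57. Five are needed.

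**4. Error when losses depend on outcome.** If a share d1 of complicated and d0 of uncomplicated patients are lost before month 4, the analysed rate is q = p(1−d1)/[p(1−d1) + (1−p)(1−d0)], and the error is P[Bin(40, q) ≤ 12] with p = 0.45. For 10%/2%: q = 0.405/(0.405 + 0.539) = 42.9%.

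| Lost, complicated / uncomplicated (assumed) | Analysed rate at a true 45% | Exact one-sided error |
|---|---|---|
| 5% / 10% | 46.3% | 2.6% |
| equal | 45.0% | 3.9% |
| 5% / 2% | 44.2% | 4.7% |
| 10% / 2% | 42.9% | 6.6% |
| 20% / 5% | 40.8% | 10.8% |

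**5. Two repairs that would fail.**
- Counting early events but still dropping event-free early leavers (d1 = 0) biases against protons. With 5% or 10% of event-free patients dropped, error falls to 2.7% or 1.8%, and exact power to 78% or 73%.
- A plain Wald test, which uses the estimated variance, rejects at 13/40: z = 0.125/√(0.325·0.675/40) = 1.69. Its exact size is P[Bin(40, 0.45) ≤ 13] = 7.5%.

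**The case against.** The strongest case on the other side has four parts, and much of it stands.

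*Early loss may be rare.* Section 5 schedules visits after surgery weekly for a month, fortnightly for a month, then monthly for three months, which spans the window. Section 2 requires pre-operative patients to have surgery at the study hospital. It also says of progression: "If recurrent or progressive cancer is diagnosed, the subject will be considered off study at that time". A reader might infer that such patients automatically drop out of the test. The documents do not support that, because the same section commits the investigators to try to follow off-study patients for toxicity. These provisions lower the chance of short follow-up. They do not change the evaluability rule, and they cannot help after a death or a refusal of contact.

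*The direction is not established.* A reader might infer that the rule favours protons because a bad wound drives patients away. Nothing in the documents shows this. A patient needing readmission or packing may stay in closer contact than one who has healed.

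*Waiting until month 4 has a purpose.* The packing component cannot be confirmed before about day 120, so not every qualifying event is known as soon as it begins. That justifies scoring at 4 months. It does not justify discarding a reoperation already on record.

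*The allowance of 50 for 40 is not an early-loss rate.* Section 6.4 counts as evaluable those who have lower-extremity disease, undergo surgery and complete 4 months. The ten extra therefore also cover patients who never have surgery, and they are not split by reason.

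**Conclusion.** The point holds as a defect of the written rule. It makes a recorded outcome depend on later retention, so known failures can leave the primary test. Whether this has a net effect, and in which direction, depends on losses that the documents do not report. Equal loss gives no bias, and the assumed scenarios run from 2.6% to 10.8% error against 3.9% with none.

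A reader might go further and put the true error at 8.5%, 11.8% or 15.9% for two, three or four excluded patients. Those values, P[Bin(40+k, 0.45) ≤ 12+k], require every excluded patient to have had a complication and no uncomplicated patient to be lost. They are worst cases, not estimates. The reversal after two restored patients likewise applies to a result at the critical value. A result at the planned alternative is much sturdier. The change is still worth making, because it is cheap and settles these cases before the data are seen.

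**What to change.** In sections 2, 6.2 and 6.3:
- Define the pre-operative primary set as all lower-extremity patients who undergo the planned resection, including those from the feasibility stage.
- Count any qualifying complication recorded within 4 months of surgery as an event, whatever the later follow-up.
- State in advance how event-free patients with under 4 months are handled, and do not drop only them. One option is a 4-month cumulative incidence that censors them at last contact and treats death without complication as a competing event. Add best-case and worst-case sensitivity analyses.
- State how the 120-day packing component is dated, since it falls at the edge of the window.
- Specify a test that holds the 5% level, based on the null variance or exact, and not a plain Wald test. The set may no longer be exactly 40, so check the exact size at the number analysed. At 41 the null-variance rule rejects at 13, with exact size P[Bin(41, 0.45) ≤ 13] = 5.9%.
- Report the 4-month-completer test as a sensitivity analysis.

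The cost is SAP wording and a little more analysis of data already being collected, with no extra patients or visits. The rate may look slightly less favourable.

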- **Partial Response (PR):** At least a 30% decrease in the sum of the longest diameters of target lesion, taking as reference the baseline sum of the longest diameters.

CONFIDENTIAL

- **Progressive Disease (PD):** At least a 20% increase in the LD of the target lesions, taking as reference the smallest sum of the LD recorded since the treatment started or the appearance any new lesion(s)
- **Stable Disease (SD):** Neither sufficient shrinkage to qualify for PR nor sufficient increase to qualify for PD, taking as reference the smallest sum LD since the treatment started.

Non-Target Lesions:

- **Complete Response (CR):** Disappearance of all non-target lesions and normalization of tumor marker levels.
- **Incomplete Response/Stable Disease (SD):** Persistence of one or more non-target lesion(s) and/or maintenance of tumor marker levels above normal limits.
- **Progressive Disease (PD):** Unequivocal progression of existing non-target lesions or any new lesion(s)

Confirmation of Response (used only for studies with response as primary endpoint)

- To assign a PR or CR, changes in tumor measurement must be confirmed by repeat assessments no less than 4 weeks after the criteria for response are first met. (*Reflect this in your study procedures table in section 6*)
- To assign SD, measurements must have met the stable disease criteria at least once after study entry at "X" interval (*as defined by protocol*).

Failure

- **Local failure** is defined as: evidence of tumor growth in any direction beyond that present of the pre-treatment imaging studies or the appearance of tumor in tissues previously scored as sites of subclinical disease. The imaging studies are to be comparable in technical factors.
- **Marginal failure** is defined as appearance of tumor growth at the margin of the target volume
- **Nodal Failure:** Failure in regional lymph nodes.
- **Distant failure** is defined as appearance of tumor at sites beyond regional nodal and marginal site.
- **Progression-Free Survival:** duration measured from first day of treatment to first documented failure, death due to any cause or last patient contact alive.
- **Overall Survival:** Duration measured from first day of treatment until death due to any cause or last patient contact alive.
- Time to local failure, time to distant failure, PFS and OS will be calculated from **first day of radiation** in the pre-operative patients and calculated from **day of surgery** in the post-operative patients.

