Publishers, 1964). Patients will be assessed for fibrosis, joint stiffness and edema within 2 years of completion of radiotherapy.

Clinical Efficacy is defined for pre-operative patients as overall response rate (CR + PR according to RECIST criteria) which is scored after radiation and before surgery. Progression-Free Survival is defined from first day of treatment to first documented failure, death due to any cause or last patient contact alive. Overall Survival is defined from first day of treatment until death due to any cause or last patient contact alive. Time to local failure, time to distant failure, PFS and OS will be calculated from first day of radiation in the pre-operative patients and calculated from day of surgery in the post-operative patients.

Rules for Early Termination for Feasibility, Acute Toxicity and Wound Complication:

Bayesian probability calculations will be employed to define rules of early termination and end of trial evaluation for feasibility and safety. The tables below indicate termination rules after groups of 3 patients have been treated. Hundreds of patients with certain types of cancer have undergone radiation therapy with protons. Thus, we will assume some "prior" feasibility and safety data for protons delivered at the standard radiation dose for our Bayesian calculations. We will assume prior information equivalent to that of 6 treated patients, which is commonly required to establish feasibility and safety in a standard 3+3 phase I trial design.

Feasibility – conducted separately for each stratum

We will assume a beta (5,1) prior, which is information equivalent to feasibility established in 5 of 6 treated patients. A feasibility rate > 90% is considered acceptable. If the number of patients deemed feasible is less than or equal to the number in the table below then termination will be considered as it is highly unlikely that the feasibility rate is > 90%, as noted by the Bayesian posterior probabilities.

Bayesian Rule for Feasibility				
Patients treated	3	6	9	12
Patients who are feasible	1	4	6	9
Posterior Prob[feasibility rate >90%]	0.0	0.0	0.0	0.0
Action	Terminate enrollment			

Acute Toxicity – conducted separately for each stratum * excludes wound complication *

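### The hypoxia–response analysis uses only RECIST responder yes/no; a pre-specified percent-change analysis should be added beside it, because the cut can lose power and the chi-square test gives no effect size

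*Combined protocol and SAP*

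**What the plan says.** Section 6.3 (Exploratory Analyses of [18F]-EF5) lists RECIST response, in pre-operative patients only, as one of the outcomes to be related to pre-treatment hypoxia. It names one method for it: "The association between RECIST response and hypoxia (binary coding) will be assessed by chi-square test". The hypoxia indicator may be "signal above versus below median signal or based on other previously defined cut points". The section also says "Both binary and continuous summary measures of" EF5 signal will be evaluated, but that sentence follows the Cox model sentence and no model for response with continuous EF5 is named.

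Response is defined in Section 6.1 (Clinical Efficacy) as "overall response rate (CR + PR according to RECIST criteria) which is scored after radiation and before surgery". Section 5 defines a partial response as "At least a 30% decrease in the sum of the longest diameters of target lesion", relative to baseline, and says "RECIST criteria will only be evaluated after radiation just prior to surgery in the pre-operative patients". The "Tumor Measurement" row of the Section 5 table is marked at pre-treatment and at the visit before surgery. The text on that visit is thinner: "This visit will involve an interval history and physical".

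The table's footnote makes the EF5 scan optional. Section 6.4 calls all the hypoxia analyses exploratory, and says that they will estimate the size of the associations for RECIST response and for the time-to-event outcomes, to guide later studies. It states no power for them.

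**The concern.** The responder cut treats a tumour that shrinks by 29% and one that grows by 19% as the same outcome, although the percent change must be worked out before either can be classified. This loss is on the outcome side, so analysing EF5 as a continuous variable does not recover it.

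The relation of hypoxia to outcome is a stated objective, and response is the only early outcome in it. The sample is small: 40 evaluable pre-operative patients at the planned size, fewer if some decline the scan. A chi-square test gives a p-value. The only effect measure that Section 6.3 names is a hazard ratio with 95% CI, which does not apply to response. As written, the plan therefore names no estimate of the quantity that Section 6.4 says will be estimated.

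**Working it through.** **1. The plan's own figure.** There is no power statement for the hypoxia–response test. The figure that fixes the pre-operative cohort at 40 is the 84% power for wound complication, 45% versus 25%, one-sided 5% (Section 6.4). With the normal approximation:

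power = Φ[(|p0 − p1|·√n − z0.95·√(p0·q0)) / √(p1·q1)] = Φ[(0.20 × 6.325 − 1.645 × 0.4975) / 0.4330] = Φ(1.03) = 84.9%.

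The exact binomial gives 82.1% (reject at 12 or fewer of 40). The stated 84% is reproduced to within 2 points, so n = 40 is a fair starting size.

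**2. Inputs for the hypoxia–response test.**
- n = 40 from Section 6.4; n = 20 as an assumed lower case, because the scan is optional and uptake is not given.
- Response rate: not in the documents; 10%, 20% and 30% assumed.
- Correlation between EF5 signal and diameter change: not in the documents; 0.4 assumed.
- Bivariate normal EF5 and diameter change, two-sided 5% test: both assumed.
- A responder is a patient in the lowest 10%, 20% or 30% of the diameter-change distribution.

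**3. Information kept by the cut.** Dichotomising a normal outcome at rate p keeps the fraction φ(z_p)² / [p(1 − p)] of the information:

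| Response rate | Information kept |
|---|---|
| 5% | 22% |
| 10% | 34% |
| 20% | 49% |
| 30% | 58% |
| 50% | 64% |

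**4. Simulated power, n = 40, correlation 0.4.**

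| Analysis | 10% | 20% | 30% |
|---|---|---|---|
| Planned chi-square, EF5 split at the median | 17% | 28% | 34% |
| Continuous EF5 by responder status (Wilcoxon) | 27% | 40% | 45% |
| Continuous EF5 by percent change (Spearman) | 69% | 69% | 69% |

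The second and third rows differ only in the outcome, so they isolate the cut:
- 10%: 69 − 27 = 42 points, 42/69 = 61% of the power.
- 20%: 69 − 40 = 29 points, 29/69 = 42%.
- 30%: 69 − 45 = 24 points, 24/69 = 35%.

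**5. Same comparison with EF5 left split at the median.** At n = 40 and correlation 0.4, moving from the chi-square test to a t-test on percent change raises power from 18%, 28% and 34% to 52–53%. The outcome effect is therefore present with either coding of EF5.

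**6. n = 20, correlation 0.4.** Chi-square gives 4%, 11% and 14%; continuous EF5 by responder status 11%, 19% and 23%; Spearman about 37%. The cut alone costs (37 − 11)/37 = 70%, (37 − 19)/37 = 49% and (37 − 23)/37 = 38% of the power. With EF5 split in both analyses and correlations of 0.3 to 0.6, the corresponding losses are 86–89%, 58–62% and 43–47%. At a 10% response rate, 0.9^20 = 12% of such trials would have no responder, and the responder comparison could not be made at all.

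**7. A different shape of relation.** Suppose hypoxia changes only the chance of crossing the 30% cut, and the size of change is otherwise unrelated to it (assumed: log-odds slope 0.8 per SD, uniform changes on each side of the cut, n = 40). At 10%, 20% and 30% response, the chi-square test then gives 16%, 29% and 38%, continuous EF5 by responder status 25%, 41% and 51%, and Spearman 13%, 23% and 37%. The advantage of percent change disappears.

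**The case against.** The strongest reply is that this is an explicitly exploratory analysis to which no alpha, power or decision is attached, and that nothing in the plan prevents a later look at percent change. That stands, and it keeps the point minor. It does not answer the gap with Section 6.4: if estimation is the purpose, an effect measure should be named in advance.

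A second reply is that the gain depends on the assumed graded relation. This also stands. Section 6.3 hypothesises a lower response rate in hypoxic tumours, and step 7 shows a link under which the responder comparison with continuous EF5 does better than percent change. That is an extreme case, but it is reason enough not to demote the responder analysis.

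A third reply is that the percent change may not be available in usable form, since the text describes the pre-surgery visit only as history and physical. The schedule does mark a tumour measurement there, and RECIST cannot be scored without one. A missing measurement would defeat the planned analysis equally.

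A reader might infer that the responder cut always costs most of the power, or take the whole gap between the planned test and the fully continuous analysis, 35 points (69 − 34) to 52 points (69 − 17), as its price. The documents support neither reading. They give no response rate, and that gap includes the median split of EF5, a separate matter that the planned continuous EF5 measure may already ease.

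**Conclusion.** The point holds as a minor improvement to an exploratory analysis. Response is related to hypoxia only through responder status, and no effect size is named for that relation. Under a graded relation with correlation 0.4, n = 40 and continuous EF5 in both analyses, the cut costs 24 to 42 points of power at response rates of 30% down to 10%. Most of the power goes only when few patients respond: about 10% at n = 40, rising to about 20% when n is near 20, where the cut costs about half or more. At higher response rates the loss is real but smaller.

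These sizes rest on an assumed correlation, response rate, bivariate normal model and two-sided 5% test, none of which the documents give. If hypoxia acts only on the chance of crossing the cut, there is little or nothing to gain. It would go too far to conclude that percent change should replace the responder analysis.

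**What to change.** In Section 6.3, keep the planned RECIST responder comparison and the CR + PR rate with its 90% CI. Add one pre-specified exploratory analysis in pre-operative patients who had the scan: the continuous EF5 summary against percent change in the sum of longest diameters from baseline to the pre-surgery measurement, reported as a Spearman correlation or a linear-regression slope with 95% CI. Use the same measurements that support the RECIST scoring, say in Section 5 how the pre-surgery one is obtained, and check that the diameters themselves are recorded and not only the response category.

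The cost is a sentence or two of wording and one more exploratory estimate to report. It needs no measurement beyond those RECIST scoring already requires, and no primary endpoint or sample size changes.
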